This will be a sequential mixed-methods study with two phases. Phase 1 will comprise a prospective, single-blinded RCT to investigate the effects of the nurse-coordinated integrated care model on various health outcomes among patients with AF. Phase 2 will comprise an exploratory qualitative study to determine how and why the intervention works. Figure 1 outlines the Phase 1 study implementation protocol. After collecting baseline data, the research nurse (RA1) will randomly allocate patients into the intervention or control group. Block randomization (block size: 8, 10, or 12) will be used to ensure even participant distribution between the two groups. The block size

and respective study group allocation sequence will be determined using a computer-generated sequence. Chronologically recruited patients will be allocated to the study groups by RA1 according to this computer-generated sequence. Participants allocated to receive the nurse-coordinated integrated care model will be provided with an appointment 1–2 weeks before their next scheduled medical appointment to initiate the intervention. The participants allocated to the control group will continue to receive conventional care as arranged by the hospital. An independent research assistant (RA2) who is blinded to the study group allocations will collect post-intervention data through medical record reviews and telephone interviews upon completion of the intervention and 6 months thereafter.

Figure 1. Study implementation protocol

Study participants

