The proposed sample size was estimated based on the primary outcome of HRQoL. To our best knowledge, no previous study examined the effect of a nurse-coordinated empowerment-based care model on AF patients. However, we have identified a few similar interventional studies targeting patients with different diseases, including diabetes[42,

43] and hemodialysis recipients.[44] Of these studies, the effect sizes of the empowerment interventions on HRQoL ranged from 0.09 to 1.17, depending on the HRQoL domains. In general, an experimental design involving a larger sample size can enable researchers to detect a smaller effect size on an outcome at a specific statistical power and significance level. However, a small effect size may not be clinically important. Therefore, after considering both the clinical relevance and previous study findings, the sample size of this study was determined to yield adequate power for the detection of at least a small to medium effect size[45] on the primary outcome. Using power analysis software package PASS 13 (NCSS, Kaysville, USA), we estimated a sample size of 176 per study arm to yield 80% power at a 5% significance level for the detection of an effect size as small as 0.3 on our primary outcome when comparing the two study arms at the post-intervention time points. After allowing for a potential dropout rate of 10%, 392 participants (196 per arm) will be recruited.

[figure not shown]
For Phase 2 of the study, a purposive sample of 30 participants from the intervention group will be invited to participate in a qualitative interview. Participants with different treatment responses to the nurse-coordinated integrated AF care model will be recruited according to changes in their post-intervention HRQoL scores. Ten participants will be selected from each range of HRQoL changes: 0–34th percentile, 35th–68th percentile, and >68th percentile.

Study interventions

Intervention group: Nurse-coordinated integrated care model for AF

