After the risk assessment, the nurse will conduct a face-to-face session in a small-group (6–8 patients/group) format to empower patients regarding decision-making and communication with physicians. This face-to-face approach was selected in accordance with literature suggesting it to be more effective than a written format.[46] Additionally, group teaching can promote peer learning and modeling. The session will begin with a structured educational session on AF and its complications, with emphasis placed on understanding the link between AF and ischemic stroke and the deleterious effects of rapid ventricular rates on cardiac function. The currently available and suitable OAC options (warfarin and NOACs) and their pros and cons (including the self-financed nature of novel OAC) as well as the rationales for rate and rhythm control will also be discussed. To assist patients with decision-making regarding OAC use, a patient decision aid developed by the National Institute of Health and Care Excellence[47] will be used. This aid organizes treatment options in an Option Grids format, wherein 10 frequently asked questions are presented vertically downwards with the options presented horizontally across the table. This format facilitates comparison and clarifies the options. Numeric and graphic formats with pictograms will be used to help patients understand the absolute and relative risks of a stroke when not using OACs or a major bleeding episode while using OACs. Patients’ individual risk profiles will be used to illustrate their stroke risks with and without OAC and their bleeding risk with OAC in a graphical format. The nurse will present the risk and benefit information in a fair and balanced manner.

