Another care component will engage patients in shared decision-making regarding OAC use by empowering them to better communicate their decisions to physicians during upcoming medical consultations. This component will highlight the key points of assertive communication, including asking questions, expressing concerns, and stating opinions and preferences regarding OACs for stroke prevention. The patients will be encouraged to generate a list of questions and concerns to propose to their physicians. To enhance patients’ confidence in their ability to maintain assertive communication in stressful situations, a series of scenario-based patient models in video format will be used to optimize the acquisition of skills for handling challenging encounters. A role-play-based rehearsal will be conducted to allow patients to practice their new skills and observe others’ behavior. The nurse will debrief patients to discuss their performance and provide feedback. Throughout the session, the nurse will adopt a supportive and non-judgmental attitude.

2. Empowerment-based group educational module

The same group of patients will attend an empowerment-based educational module beginning 1 week after their medical appointments. The module will comprise five weekly educational sessions covering the following major topics related to AF self-care: i) medication management, ii) symptom monitoring, iii) crisis management, iv) activities and exercise, and v) risk factor management to reduce risks of stroke and bleeding. The educational content of each session will comply with the recommendations of major practice guidelines for AF management.[9, 12]

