During each session, the nurse will implement the empowerment process (Table 1) to enhance patients’ knowledge, skill acquisition, and confidence in AF self-care. The empowerment approach emphasizes the use of interactive teaching strategies, experiential learning, and self-reflection during the educational process to optimize learning.[37] First, the nurse will deliver a structured educational session about the topic of the week. Emphasis will be placed on assisting patients with understanding the links between their self-care behaviors and health consequences to ensure that they appreciate the importance of their own efforts in managing AF. The nurse will encourage patients to share their current practices, and facilitate them to identify discrepancies between the suggested self-care and their current practices. The nurse will also highlight possible health consequences of these discrepancies and assist patients with setting self-directed goals related to those areas. After goal-setting, a subsequent interactive skill-building session will ensure that patients acquire the skills required to perform specific self-care behaviors. For example, to enhance patients’ confidence regarding crisis management, a series of scenario-based patient models in video format will be used to optimize the acquisition of skills needed to handle challenging encounters related to possible crises, such as a major bleeding event or suspected stroke episode. A role-play-based rehearsal will be conducted, and the nurse will discuss the patients’ performances and provide feedback. The nurse will make use of group dynamics by encouraging peer discussions of successful self-care actions, feelings, concerns, and perceived

barriers to goal achievement. The nurse will also work with the patients to mutually develop action plans for achieving goals set during each weekly educational session. Each subsequent session will begin with a discussion of progress in goal attainment. Challenges and barriers faced while implementing the action plans set during the previous week will also be discussed.

Table 1. The empowerment process.

5-step empowerment process	Intervener's counseling techniques for the empowerment process

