<pre> graph TD A[Peer sharing & address concerns] --> B[Skill building] B --> C[Structured education] C --> D[Self-reflection & goal setting] D --> E[Action planning] E --> B </pre>	
 Be supportive to assist patients to identify their inadequacy in self-care Avoid judgmental attitudes Be patient-centered in identifying the barriers to self-care Use active listening to identify concerns, fears and beliefs that may hinder effective self-care Be collaborative with the patients to work through ambivalence to set patient-directed goals Use reflection and paraphrasing to validate patients' feelings and their capacities to solve problems Be respectful to the expertise of patients Genuinely believe in patients' ability to make the changes Acknowledge patients' right and responsibility to make self-care choices and to be the primary decision makers

3. Nurse-initiated telephone support

The nurse will provide continued support by telephone after the face-to-face sessions have been completed (two weekly and two bi-weekly calls). A telephone record containing patients' clinical profiles, AF-related treatments, self-management goals, and action plans will be used to facilitate the process. The nurse will monitor patients' adherence, symptom profiles, treatment efficacies, adverse effects, and goal attainment progress; identify barriers in the self-care process; and provide resolutions and continued support via the telephone. Health counseling and advice given will be documented to guide subsequent telephone correspondence.

4. Patient-initiated contact for professional advice

All participants from the intervention group will be provided with telephone access to the nurse for inquiries regarding disease management during office hours. The nurse will provide health advice and counseling accordingly. For severe undesirable symptoms and adverse reactions to medications, the nurse will attempt to advance patients' follow-up appointments or advise patients to seek emergency medical care if necessary. All correspondence and advice given will be documented in patients' profiles.

Control group: Conventional care

The control group will receive the conventional care provided by the study hospital.

Fidelity monitoring of the study intervention

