Multiple methods will be used to monitor the fidelity of the study interventions. Assessment and record forms will be used to document the care activities provided to patients during the sessions, telephone calls, and patient-initiated contacts. The nurse will file these assessment records to facilitate care coordination. Care activities will be coded, tracked, and checked against the intervention protocol. A standardized manual will be developed to guide the delivery of each group-based education session. Moreover, the PI will randomly select five groups in the intervention arm for monitoring. Face-to-face sessions will be videotaped after obtaining the participants' consent. Two research

fellows will review the tapes and complete a performance checklist after a briefing session by the PI. In addition, the nurse will document reflective notes after each session and hold monthly discussions with the investigation team. Participants' attendance will be recorded. All these data will be submitted for interpretation.

Outcome measures

The following instruments will be administered at baseline, upon completion of the intervention, and 6 months thereafter.

Compatibility between patient and physician decisions

Patients will be asked to indicate whether a decision regarding the choice of OAC was made before the consultation and, if yes, details of the choice.[48] The physician's prescription of any OACs will be monitored after the consultation. The nurse will confirm prescriptions with the patients and trace prescription record information in the Hospital Authority's Clinical Management System. The patients' choices and physicians' prescription decisions will be examined to determine compatibility.

8-item Morisky Medication Adherence Scale (MMAS-8)

The MMAS-8 will be used to assess self-reported medication adherence.[49] Each item measures a specific medication-taking behavior using a dichotomous (yes/no) response (Items 1–7) or a 5-point Likert scale (Item 8). The scores range from 0 to 8, with higher scores indicating better adherence. The Chinese version yields acceptable internal consistency (Cronbach's $\alpha = 0.77$), good test-retest reliability ($r = 0.88$), and construct validity.[49]

Atrial Fibrillation Effect on QualiTy-of-life (AFEQT) Questionnaire

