The 20-item AFEQT[50] measures disease-specific HRQoL in AF patients using 4 subscales: symptoms, daily activities, treatment concerns, and treatment satisfaction. All subscales are rated on a 7-point Likert scale, with higher scores indicating a poorer HRQoL. The subscales' Cronbach's alphas ranged from 0.88 to 0.95, the test-retest reliability and construct validity are satisfactory, and the instrument is responsive to treatment.[50] This investigation team developed the Chinese version of the AFEQT, which is currently undergoing psychometric validation.

Hospital Anxiety and Depression Scale (HADS, Chinese-Cantonese version)

The 14-item Chinese-Cantonese version of the HADS[51] will be used to measure anxiety and depression. This instrument is rated on a 4-point Likert scale, with higher scores indicating more intense anxiety and depression. The HADS is reported to have good internal consistency (Cronbach's alpha = 0.86) and satisfactory factorial, concurrent, and criterion validity.[51]

Data analysis

The statistical analysis of the outcome comparisons will be performed based on the intention-to-treat principle. Variables with skewed data will be transformed appropriately prior to analysis. Baseline characteristics between the two study arms will be compared using the t-test or chi-square test where appropriate. A mixed-effects model will be used to compare differential changes in the outcome variables over time and between the two arms. The mixed-effects model can account for intra-correlated repeated-measures data and produce unbiased estimates even if some data are missing, as long as the data are missing at random. All statistical analyses will be performed using SAS version 9.4 (SAS Institute, Cary, NC). All statistical tests will be 2-sided, with a significance level of 0.05.

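### Intervention patients are taught in fixed groups of 6–8, but neither the sample size nor the described model allows for correlation within groups, so 5% error and 80% power are not assured

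*Combined protocol and SAP*

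**What the plan says.** Under Study design, allocation is by individual patient: "Chronologically recruited patients will be allocated to the study groups by RA1 according to this computer-generated sequence".

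Under Study interventions, intervention patients are then grouped. For the decision-making session, "the nurse will conduct a face-to-face session in a small-group (6–8 patients/group) format". The groups stay together: "The same group of patients will attend an empowerment-based educational module beginning 1 week after their medical appointments", and that module has five weekly sessions. Interaction within the group is an intended mechanism: "The nurse will make use of group dynamics by encouraging peer discussions of successful self-care actions". The fidelity section treats groups as identifiable units: "the PI will randomly select five groups in the intervention arm for monitoring".

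Controls are not grouped: "The control group will receive the conventional care provided by the study hospital".

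The sample-size paragraph (under Study participants) says "we estimated a sample size of 176 per study arm to yield 80% power at a 5% significance level" for an effect size of 0.3 on health-related quality of life. It then allows 10% dropout, giving 196 per arm and 392 in total. It mentions no ICC, group size or design effect.

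Data analysis plans a mixed-effects model for change over time and between arms and says "The mixed-effects model can account for intra-correlated repeated-measures data and produce unbiased estimates even if some data are missing". It does not list the random effects and does not mention teaching groups.

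**The concern.** This is a partially nested design: individual randomisation, with clustering created by treatment delivery in one arm only. Patients who share six group sessions, peer discussion and jointly developed action plans may end up with more similar outcomes than patients in different groups. A patient-level random effect covers the correlation between one patient's visits. It does not absorb variation between groups that arises after baseline.

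There are two separate consequences:

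- **Groups left out of the model.** Any positive post-baseline ICC makes the standard error of the arm comparison too small, the confidence interval too narrow and the type I error higher than 5%. The point estimate is not biased by this.
- **Groups modelled.** The error returns to about 5%, but the comparison used for sizing has less than 80% power unless baseline adjustment makes up the loss.

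**Working it through.** **Inputs from the documents:** effect size d = 0.3 (SD = 1), two-sided 5%, 80% power, 176 analysed per arm, 10% dropout, groups of m = 6–8.

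**Assumed, because the documents do not give them:** ICC 0.01, 0.02, 0.05 or 0.10; m = 7 as the central case (176/7, about 25 groups); equal total variance in both arms; and, where used, a baseline–follow-up correlation ρ.

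**1. The plan's own figure.** n = 2(1.96 + 0.8416)²/0.3² = 174.4 per arm. The t-test version gives 175.4, rounded up to 176, with 80.1% power. Then 176/0.9 = 195.6, so 196 per arm and 392 in total. The plan's figures are reproduced exactly under independence, with no spare margin.

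**2. Groups omitted.** The intervention-arm variance is multiplied by DE = 1 + (m − 1)·ICC; the control arm is unchanged. The ratio of true to naive standard error is √[(1 + DE)/2], and the actual type I error is 2Φ(−1.96/ratio).

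At m = 7 and ICC 0.05: DE = 1.30, ratio = √1.15 = 1.072, 1.96/1.072 = 1.828, error = 6.8%.

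**3. Groups modelled, single unadjusted post-intervention contrast.** SE = √[(1 + DE)/176]. Power comes from the noncentral t with Satterthwaite degrees of freedom.

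At ICC 0.05: SE = √(2.30/176) = 0.114, 0.3/0.114 = 2.62, df = 70, power = 73.5%.

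| ICC (m = 7) | True/naive SE | Error, groups omitted | Power, groups modelled (df) | Detectable d at 80% | n per arm for 80% at d = 0.3 (recruits) |
|---|---|---|---|---|---|
| 0.01 | 1.015 | 5.3% | 78% (81) | 0.307 | 184 (410) |
| 0.02 | 1.030 | 5.7% | 77% (78) | 0.311 | 190 (424) |
| 0.05 | 1.072 | 6.8% | 73.5% (70) | 0.325 | 206 (458) |
| 0.10 | 1.140 | 8.6% | 68% (60) | 0.346 | 233 (518) |

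At ICC 0.05, groups of 6 to 8 give error 6.5–7.1%, power 75–72%, and 448–470 recruits for 80%.

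**4. Simulation check.** With 25 groups of 7 against 176 controls, the ungrouped test rejected a true null in 5.5%, 5.7%, 6.9% and 8.3% of trials at the four ICCs. A group-level test held 4.9–5.2%, with power 77.8%, 77.1%, 72.8% and 68.1%.

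**5. With baseline adjustment.** Here the group variance is held fixed on the raw scale and baseline removes only individual variance: Var = {[(1 − ρ²) + (m − 1)·ICC] + (1 − ρ²)}/176. At ρ = 0.5 and ICC 0.05 this is (1.05 + 0.75)/176, so SE = 0.101 and power is 83%. The SE ratio is √(1.80/1.50) = 1.095, so the error if groups are omitted is 7.4%. Across the four ICCs, power with groups modelled is 88%, 87%, 83% and 77%; error with groups omitted is 5.5%, 5.9%, 7.4% and 9.8%. The ρ needed to bring modelled-group power back to 80% is about 0.21, 0.28, 0.41 and 0.57.

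**The case against.** - **The ICC is unknown and could be small.** The documents refer to the nurse in the singular, a standardised manual guides the sessions, the last phase is individual telephone support, and outcomes are measured again 6 months later. Nothing in the documents favours 0.05–0.10 over 0.01–0.02, where the error is at most 5.8%. This stands as a limit on the size of the problem. It is also a reason to state an assumption.
- **The planned model compares changes over time.** A group difference already present at baseline and constant thereafter cancels from that contrast, so only correlation arising after baseline matters. This is right, and the claim is limited accordingly. Group teaching would produce exactly that kind of correlation.
- **The power figures are for an unadjusted contrast.** They match the plan's sizing but not necessarily its model. For a change score at ICC 0.05, power is about 61%, 74%, 81% and 89% at ρ = 0.3, 0.5, 0.6 and 0.7. Power under the planned analysis is therefore unknown.
- **The baseline-adjusted figures depend on the ICC scale.** If the ICC is defined on the residual scale, at ρ = 0.5 the error stays at 5.3/5.7/6.8/8.6% and power is 89/88/85/80%. The extra inflation in step 5 is specific to the raw scale.
- **The dropout allowance may help.** If all 196 per arm were analysed, modelled-group power would be about 81–83% at ICC 0.01–0.02, but 77–79% at 0.05 and 71–75% at 0.10 (groups of 6–8). Type I error would not improve.
- **The random effects are not listed.** A group term is unspecified, not ruled out. But a prespecified analysis should not leave open a choice that changes the standard error of the primary comparison.

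**Conclusion.** The concern holds in its conditional form. If group teaching induces correlation after baseline, the analysis as described is anti-conservative, and the stated 80% power is not secured. At ICC 0.01 the effect is minor (error about 5.3%, power about 78%). At 0.05–0.10 it is material (error 6.8–8.6%, power 73.5–68%). These figures assume 176 analysed per arm, groups of 7 and no baseline adjustment. The omission itself is certain; its size is not, because the documents give no ICC. The size can also differ by outcome: the compatibility outcome follows only the first group session, and the figures here are for a continuous outcome. This should be fixed before analysis; it does not bias the treatment estimate.

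**What to change.** 1. **Data analysis.** Prespecify a random effect for assigned teaching group in the intervention arm only, with controls as singletons, in addition to the within-patient covariance, and use Kenward-Roger or Satterthwaite degrees of freedom. Let the group effect act on post-baseline visits, or use baseline as a covariate. If baseline is one of the outcome visits, a group intercept constant from baseline cancels from the arm-by-time contrast and corrects nothing. In a check at ICC 0.10 (48 model fits), such a model gave a mean SE of 0.106, against a naive 0.107 and a true 0.122.
2. **Data collection.** Record the assigned group for every intervention patient, including those who do not attend.
3. **Sample size.** State the assumed ICC and group size and restate the power or detectable effect. At ICC 0.05 without baseline adjustment, for example: about 73–74% at d = 0.3, or 80% at d of about 0.32–0.33. The alternative is to prespecify baseline adjustment and give power under a stated correlation and ICC scale (about 83% at ICC 0.05 and ρ = 0.5, raw scale).

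The cost is some wording, one group variable and one model term. No extra patients are needed if power is restated or baseline adjustment is prespecified. The price is a slightly less favourable stated power and fewer effective degrees of freedom (about 60–80 at groups of 7). Restoring 80% at d = 0.3 by recruitment alone would take about 448–470 patients at ICC 0.05, against 392 planned; prespecified baseline adjustment is the cheaper route.
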